**Table 4: Schedule of Assessments**

Phases/Visits  Tasks / Events	Screening		Double-blind Treatment Phase					Early Termination	Safety Follow-Up
	Visit 1 Screening	SAFER	Day 1	Week 2	Week 4	Week 6	Week 8		
			Stage 1						
			Stage 2						
Days relative to start dosing of study drug	-28 to -14	-14 a	1	14 x	28 a	42 x	56 a	NA	63 ap
ENTRY / SAFETY / ADMINISTRATIVE									
Informed consent	X								
Inclusion/exclusion criteria	X	X j	X						
Demographics / habits b	X								
Medical/psychiatric history	X		X						
PTSD diagnosis (CAPS-5)	X								
SAFER interview (Confirmation of PTSD diagnosis and overview of inclusion/exclusion criteria)		X j							
LEC-5 (Part of PCL-5 with LEC-5 and Criterion A)	X								
S-STSW	X s		X u	X uw	X u	X uw	X u	X u	
Vital signs c	X		X	X	X	X	X	X	X r
Height	X e								
Weight	X e		X	X	X	X	X	X	X r
Physical examination	X				X		X	X	X r
12-lead ECG d	X		X		X		X	X	X r
Randomization			X		X				
Prior and concomitant medications w	X		X	X w	X	X w	X	X	X
Study drug dispensing o			X	X	X	X			
Study drug administration			X k	X	X l	X	X		
Study drug compliance monitoring f			X	X	X	X	X	X	
Adverse events ew	X	X	X	X w	X	X w	X	X	X
LABORATORY TESTS									
Clinical chemistry q	X		X	X	X	X	X	X	X r
Hematology	X		X		X		X	X	X r
HIV and hepatitis tests	X								

Pregnancy test v	X h		X i		X i		X i	X i
Drug and alcohol screen	X h		X i		X i		X h	X h
Urinalysis	X		X		X		X	X
Clinical Measures								
CAPS-5 w	X s		X t	X tw	X t	X tw	X t	X t
PCL-5	X s		X t	X t	X t	X t	X t	X t
HADS t	X		X	X	X	X	X	X
CGI-S	X		X	X	X	X	X	X
PSQI	X		X	X	X	X	X	X
PSQI-A	X		X	X	X	X	X	X
DES-II			X		X		X	X
BAC-Symbol Coding			X		X		X	X

Abbreviations: BAC-Symbol Coding = Symbol Coding from the Brief Assessment of Cognition; CAPS-5 = Clinician Administered PTSD Scale for DSM-5; [REDACTED] CGI-S = Clinical Global Impression – Severity; DES-II = Dissociative Experiences Scale-II; DNA = Deoxyribonucleic acid; ECG = electrocardiogram; HADS = Hospital Anxiety and Depression Scale; HIV = human immunodeficiency virus; LEC-5 = Life Events Checklist for DSM-5; [REDACTED] PCL-5 = PTSD Checklist for DSM-5; [REDACTED] PSQI = Pittsburgh Sleep Quality Index; PSQI-A = Pittsburgh Sleep Quality Index Addendum; PTSD = Post-Traumatic Stress Disorder; SCID-5-CT = Structured Clinical Interview for DSM-5 (Clinical Trials Version); [REDACTED]; S-STIS = Sheehan Suicidality Tracking Scale.

- a) Visit window is ± 3 days.
- b) Includes alcohol or illicit drug use history, employment status, smoking history, and index traumatic event.
- c) Collect vital signs after at least 5 minutes of rest, seated or supine.
- d) ECG after at least 5 minutes supine rest.
- e) Include body mass index calculation.
- f) Subjects use smartphone video application monitoring. Investigative site personnel calculate compliance and document accountability via capsule count/blister package inspection.
- g) Serious Adverse Event (SAE) reporting begins at time of informed consent and continues until 30 days after the last dose of study drug. Non-serious AE collection commences with the time of first dose of study drug until last day of subject participation in the study.
- h) Serum sample.
- i) Urine sample or breathalyzer (alcohol screen).
- j) Via phone.
- k) Doses are to be administered at the clinic on Day1 (after completing other procedures) then on an outpatient basis.

- l) Stage 2 dosing begins on the day after the Week 4 visit.
- m) Includes concurrent medical and psychiatric history.
- n) [REDACTED]
- o) Use interactive response technology for study drug dispensing.
- p) 7 days post-therapy.
- q) Clinical labs should be fasted except for screening.
- r) Only if required for adverse event follow-up.
- s) Rating based on the past month
- t) Rating based on the past week
- u) Use “since last visit” version after screening.
- v) Women of childbearing potential.
- w) Remote visit (optional. Only if necessary, due to COVID-19 health emergency)
- x) Visit window is  $\pm 7$  days.

## 7.2. Scientific Rationale for Study Design

This Phase 2, proof-of-concept, placebo-controlled study uses a sequential parallel comparison design (SPCD), which is appropriate due to the short active treatment phases (two 4-week double-blind treatment periods) and the expected relatively meaningful placebo response rate. The purpose of conducting this exploratory study is to investigate the safety and tolerability of NYX-783 in a PTSD population, and to characterize the response profile of NYX-783 for the treatment of PTSD symptoms evaluated by the intrusion, avoidance, negative alterations in cognition and mood, and arousal & reactivity subscores as well as CAPS-5 total score. The results from this study will be utilized to inform the future NYX-783 development plans.

The SPCD is an adaptive design that allows for re-randomization of placebo subjects (both "non-responders" and "responders") from an initial stage of the study to placebo or active treatment in a subsequent stage of the trial. In this study, data from the "all-comers" population of Stage 1 arms [1 = placebo], [2 = NYX-783 50 mg QD], [3 = NYX 783 10 mg QD] and the subpopulations of "placebo non-responders" in Stage 2 arms [7 = placebo], [8 = NYX-783 50 mg QD], [9 = NYX 783 10 mg QD] are pooled to yield a single p-value for treatment comparison. Estimation of the treatment effect is enhanced by using data from the two study stages (Tamura 2011), and the SPCD design is appropriate for earlier stage trials, such as moderately-sized Phase 2 studies. (Tamura 2011, Baer 2013) The SPCD design aims to increase the probability of demonstrating a treatment effect, especially if the Stage 1 placebo response rate is high. (Chen 2011) The design reduces the impact of placebo response and thus improves the power of the study, which in turn allows for an adequately powered proof-of-concept trial with a smaller sample size and mitigation of the untoward effect of a placebo response. (Baer 2013) All efficacy analyses will be evaluated at the 0.10, one-sided  $\alpha$  level. One-sided is appropriate because the primary objective of the study is to demonstrate that NYX-783 is superior to placebo in reducing the severity of PTSD symptoms.

Beyond the primary objective, an SPCD can address useful exploratory aspects. In this study, for example, by providing information about the maintenance effect of NYX-783 treatment after re-randomization of subjects initially allocated to one of the active treatment arms [2] and [3] to placebo arms [10] and [11]. The re-randomization of both placebo-responders and placebo non-responders from Stage 1 will characterize the response profile of subjects with initial high vs. low placebo response rate in Stage 2 drug treatment arms [5], [6] vs. [8], [9] respectively.

Altered gene expression associated with PTSD has been characterized in peripheral blood samples collected from civilian and military populations in clinical trials. (Banerjee 2017) Analysis of RNA, including microRNA (miRNA) and/or messenger RNA (mRNA), provides a new opportunity to understand the biological pathways underlying PTSD, with the potential to establish biomarker-driven subgroups within the PTSD diagnosis, and/or to serve as a platform for pre-clinical mechanistic studies (Glatt 2013).

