## **8. SELECTION AND WITHDRAWAL OF SUBJECTS**

### **8.1. Subject Inclusion Criteria**

In order to be eligible to participate in this study, an individual must meet all of the following criteria:

1. Male and female subjects between the ages of 18 to 65 years (inclusive) at the time of signing the informed consent.
2. A primary diagnosis of PTSD (DSM-5 criteria, APA 2013) according to the CAPS-5 and SCID-5-CT, with the primary traumatic event occurring  $\geq 12$  months prior to screening. NOTE: In cases of “delayed--onset PTSD,” clinically manifest PTSD symptoms must be present for at least 6 months prior to screening.
3. PCL-5  $\geq 38$  at screening.
4. CAPS-5 total score  $\geq 30$  at screening.
5. Qualified to participate according to the SAFER interview.
6. Female subjects of childbearing potential must have a negative serum pregnancy test at screening and be practicing an adequate method of birth control (e.g., oral or parenteral contraceptives, intrauterine device, barrier, abstinence). Subjects may not be breastfeeding or plan to become pregnant or donate ova during the study and for 30 days after the last dose of study drug.
7. Male subjects who are sexually active with female partner(s) must agree to the following during the study and for 30 days after the last dose of study drug: a) use an acceptable method of birth control (condom with spermicide or surgical sterilization) and b) refrain from sexual activity with female partners who do not use an acceptable method of birth control. Barrier contraception (condom with spermicide) **must** be used by all male subjects who are not surgically sterilized at least 90 days prior to screening. Male subjects must also agree to refrain from sperm donation during the study and until 30 days after the last dose of study drug.
8. Ability to understand the requirements of the study, provide written informed consent, abide by the study restrictions, and agree to return for the required assessments.
9. Willing to use a smartphone-based video recording technology for monitoring compliance with study drug administration.
10. The subject has a stable social situation in the investigator’s opinion, e.g. no changes are expected during the course of the study in work, marital, or accommodation status.

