### 10.2. Randomization and Blinding

The study will be conducted as a placebo-controlled, double-blind study. The randomization schedule will be produced by the authorized sponsor designee.

On Day 1, subjects will be randomized to receive placebo, NYX-783 50 mg QD, or NYX-783 10 mg QD in a 4:1:1 ratio, respectively. Placebo responders and placebo non-responders (CAPS-5 total score reduction from baseline  $\leq 35\%$  and total CAPS-5 total score  $\geq 26$  at Week 4) will be identified at the completion of Stage 1 (Weeks 1-4) in a blinded fashion; then, each group (i.e., placebo responders and placebo non-responders) will be re-randomized in a blinded fashion to placebo, NYX-783 50 mg QD, NYX-783 10 mg QD in a 3:2:2 ratio, respectively, for Stage 2 (Weeks 4-8) treatment. Subjects who received active treatment during Stage 1 will receive placebo in Stage 2.

The authorized investigative site personnel will obtain blinded kit assignments using an interactive response technology (IRT) system. The blinded dose information may only be obtained by the investigator (or designee) in an emergency, where the information may have an impact on further treatment decisions or aid in the emergency treatment of the subject. Every effort must be made to contact the sponsor prior to unblinding.

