### **3.5. Method of Assigning Subjects to Treatment Groups**

On Day 1, subjects will be randomized to receive placebo, NYX-783 50 mg QD, or NYX-783 10 mg QD in a 4:1:1 ratio, respectively. Placebo responders and placebo non-responders (CAPS-5 total score reduction from baseline  $\leq 35\%$  and total CAPS-5 total score  $\geq 26$  at Week 4) will be identified at the completion of Stage 1 (Weeks 1-4) in a blinded fashion; then, each group (i.e., placebo responders and placebo non-responders) will be re-randomized in a blinded fashion to placebo, NYX-783 50 mg QD, NYX-783 10 mg QD in a 3:2:2 ratio, respectively, for Stage 2 (Weeks 4-8).

treatment. Subjects who received active treatment during Stage 1 will receive placebo in Stage 2.

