**Figure 1: Study Design**

\* Placebo non-responder: CAPS-5 reduction from baseline ≤ 35% and CAPS-5 total score ≥ 26 at Week 4.

BAC Symbol Coding, Symbol Coding from the Brief Assessment of Cognition; CAPS-5, Clinicians Administered PTSD Scale for DSM-5; [REDACTED] CGI-S, CGI-Severity; HADS, Hospital Anxiety and Depression Scale; LEC-5, Life Events Checklist for DSM-5; PCL-5, PTSD Checklist for DSM-5; PSQI, Pittsburgh Sleep Quality Inventory; PSQI-A, PSQI-Addendum for PTSD; SCID-5, Structured Interview for DSM-5; [REDACTED] S-STS, Sheehan Suicidality Tracking Scale. ☎ Phone Interview

Figure from protocol Section 7.1 Overall Study Design and Plan: Description.

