## 4. Statistical Analysis and Reporting

### 4.1. Introduction

Data processing, tabulation of descriptive statistics, calculation of inferential statistics, and graphical representations will be performed primarily using SAS (release 9.4 or higher).

Continuous (quantitative) variable summaries will include the number of subjects (n) with non-missing values, mean, standard deviation (SD) (or standard error (SE) if appropriate), median, minimum, and maximum. Confidence intervals (CIs) will be added if appropriate.

Categorical (qualitative) variable summaries will be based on frequencies and percentages.

Unless stated otherwise, efficacy data for endpoints included in mixed effects repeated measures model (MMRM) analyses (groups [1], [2], [3], [7], [8], and [9]) will be summarized by visit and treatment group (Placebo, NYX-783 10 mg QD, NYX-783 50 mg QD) to allow for summary data treatment comparisons as per model inference.

Efficacy data for Stage 2 groups [4], [5], [6], [10], and [11] will be presented separately.

Unless stated otherwise, safety data will be summarized by Stage and treatment group (Placebo [as Placebo Only and Placebo Stage 2, separately], NYX-783 10 mg QD, NYX-783 50 mg QD); data presented by visit will be displayed based on the treatment group which applies at onset for AEs/collection date.

The minimum and maximum will be reported with the same degree of precision (i.e., the same number of decimal places) as the observed data. Measures of location (mean and median) will be reported to 1 degree of precision more than the observed data and measures of spread (SD, SE) will be reported to 2 degrees of precision more than the observed data.

Percentages will be presented to 1 decimal place, unless otherwise specified.

Unless otherwise indicated, all statistical tests will be conducted at a 0.10 significance level using one-sided tests and p-values will be reported. Corresponding 80% CIs (the interpretation of which is equivalent to a one-sided 90% CI when restricted to a single bound) will be presented.

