## 6. General Issues for Statistical Analysis

### 6.1. Statistical Definitions and Algorithms

#### 6.1.1. Baseline

The last non-missing observation recorded prior to the first dose of study drug (NYX-783 or placebo) will be used as the baseline observation for all calculations of change from baseline for Stage 1 data. For purposes of safety evaluation, subjects that are re-randomized in Week 4, the last non-missing observation before Week 4 will be used as baseline for Stage 2 data, with exception of groups [4] and [7] as referenced in [Figure 1](#). Changes from baseline for these groups will be based on the Stage 1 baseline given their study intervention remained unchanged.

For purposes of efficacy analyses, baseline values for Stage 2 data within all groups [4], [5], [6], [7], [8], [9], [10], and [11] will be based on the last assessment prior to first dose of study drug in Stage 2.

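### The exploratory comparison of drug arms 5 and 6 with drug arms 8 and 9 is biased by regression to the mean; each stratum should be read against its own placebo arm

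*Protocol*

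**What the plan says.** Protocol 7.2, among the exploratory uses of the design, says that re-randomising Stage 1 placebo responders and non-responders will characterise "the response profile of subjects with initial high vs. low placebo response rate in Stage 2 drug treatment arms [5], [6] vs. [8], [9"]. Arms 5 and 6 are the drug arms among responders, and arms 8 and 9 the drug arms among non-responders. The placebo arms of the two strata, 4 and 7, are not mentioned in that sentence.

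Only the non-responder is defined, in two parts joined by 'and'. SAP Figure 1 has: "Placebo non-responder: CAPS-5 reduction from baseline ≤ 35% and CAPS-5 total score ≥ 26 at Week 4". SAP 6.1.4 and Protocol 10.2 agree. Every other re-randomised placebo subject is therefore a responder. (The legend to Protocol Figure 1 prints the Week 4 threshold with the inequality reversed. The two must be reconciled, since the rule defines the strata.)

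The entry severity criterion is "CAPS-5 total score $\geq 30$ at screening" (Protocol 8.1); no Day 1 minimum is stated. For efficacy, SAP 6.1.1 says that Stage 2 baselines "will be based on the last assessment prior to first dose of study drug in Stage 2", in practice the Week 4 score.

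SAP 3.5 says that "each group (i.e., placebo responders and placebo non-responders) will be re-randomized in a blinded fashion", and Protocol 10.2 gives a 3:2:2 ratio, so each stratum has a concurrent randomised placebo arm. SAP 4.1 adds: "Efficacy data for Stage 2 groups [4], [5], [6], [10], and [11] will be presented separately". Protocol 14.4.1 makes arms 4, 5, 6, 10 and 11 exploratory.

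**The concern.** Non-responders are selected partly because their Week 4 score was high, and Stage 2 change is measured from that same score. Chance variation in one assessment therefore enters both the selection and the outcome. Non-responders tend to drift down by Week 8 and responders to drift up, whatever they take. A comparison of arms 5 and 6 with arms 8 and 9 adds this drift to any drug effect and cannot separate the two.

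The stratum label is a second problem. Protocol 7.2 treats arms 4 to 6 as the high placebo response group, but the complement of a two-part rule also takes in people who crossed the score threshold with a small fall.

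Protocol 7.2 says that the results will inform further development. A reader of the stated comparison could conclude that the drug works better in placebo non-responders when it does nothing in either group, and could enrich the next trial on that basis.

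**Working it through.** **Plan's own figure.** The documents give no figure for this comparison. The only design figure, about 80% power, is not in dispute. It cannot be reproduced, because the effect size, SD and placebo response rate are not stated.

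**Direction, without numerical assumptions.** Write the Week 4 score as T + e4. With no drug effect and no true Stage 2 change, the Week 8 score is T + e8, where e4 and e8 are independent visit-level errors. Then:

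- Change = e8 − e4, so mean change in a stratum = −(mean of e4 in that stratum).
- Selection on a high Week 4 score makes mean e4 positive in non-responders, so they fall. It is negative in responders, so they rise.
- Adjusting for the Week 4 score does not fully remove the gap. At the same Week 4 score of 26 or more, responders are those with the higher Day 1 score, and so with a higher expected T.
- Within a stratum, randomisation gives e4 the same distribution in every arm, so drug minus placebo has expectation 0.

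**Size, by simulation with no drug effect.** All inputs below, other than the CAPS-5 ≥30 screening cut and the stratum rule, are assumed.

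- Set A: mean screening score 38 or 42 before the cut, SD 9, visit-to-visit correlation 0.7 or 0.8, mean Stage 1 placebo fall 6 or 10 points with between-subject SD 7.
- Set B (wider): true mean 38 or 42, true SD 8, single-visit reliability 0.6 to 0.9, Stage 1 placebo fall 8 points with SD of true change 0 or 8.

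| Quantity with no drug effect | Set A | Set B |
|---|---|---|
| Gap in raw Week 4 to 8 change, favouring non-responders (points) | 2.8 to 4.4 | 1.3 to 8.7 |
| Gap after adjusting for the Week 4 score (points) | 0.9 to 1.5 | 0.4 to 3.6 |
| Responders with a reduction of 35% or less | 13% to 32% | 14% to 68% |

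The Set A gaps use integer scores; its share spans runs with integer and continuous scores. In Set B, 2% to 14% of responders had a reduction of 20% or less. The difference of within-stratum contrasts, (arms 5, 6 minus 4) minus (arms 8, 9 minus 7), lay between −0.10 and +0.07 points, which is simulation noise.

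**The responder rule.** CAPS-5 is a sum of integer items, and a score of 26 still satisfies the non-responder threshold. The highest Week 4 score that makes a responder on the threshold alone is therefore 25. The percentage fall is (B − 25)/B for Day 1 score B:

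| Day 1 score B | Fall to 25 |
|---|---|
| 28 | 3/28 = 10.7% |
| 30 | 5/30 = 16.7% |
| 32 | 7/32 = 21.9% |
| 38 | 13/38 = 34.2% |
| 39 | 14/39 = 35.9% |

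From a Day 1 score of 38 or below, reaching 25 classes the subject as a responder with a fall under 35%. With no Day 1 minimum, a score of 25 that stays at 25 also qualifies.

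**Arm sizes.** Stage 1 placebo: 156 × 4/6 = 104. After 15% dropout: 104 × 0.85 = 88.4. With an assumed responder share p, arm 4 holds 88.4 × p × 3/7 and arms 5 and 6 hold 88.4 × p × 2/7 each. Arms 7 to 9 use 1 − p.

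| Assumed p | Arms 4 / 5 / 6 | Arms 7 / 8 / 9 |
|---|---|---|
| 20% | 7.6 / 5.1 / 5.1 | 30.3 / 20.2 / 20.2 |
| 50% | 18.9 / 12.6 / 12.6 | 18.9 / 12.6 / 12.6 |

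These are numbers entering Stage 2, before its assumed 11% dropout.

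**The case against.** The sentence in Protocol 7.2 is design rationale. It offers an example of an exploratory use and names no endpoint, estimator or test. That stands: a reader might infer that a formal active-only test is planned, and the visible text does not say so.

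The exploratory analyses are largely withheld. Protocol 14.4.1.3 is in the contents but not in the visible body, and the visible part of SAP 8.3 begins at 8.3.5. A reader might infer that no within-stratum contrast exists anywhere. That cannot be concluded from text that is not shown.

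It might also be inferred that presenting arms 4 to 6 apart, as SAP 4.1 does, is part of the fault. It is not: that layout keeps arms 5 and 6 beside their own placebo arm. SAP 11 further calls a comparison of active groups not relevant without results against placebo. This most naturally means one dose against the other, and it neither names nor withdraws the reading in Protocol 7.2.

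The visible MMRM adjusts for baseline, so the raw gap overstates what an adjusted comparison would show. This is correct, and the adjusted range is given for that reason; it is smaller but not zero. Finally, arms 5 and 6 may hold about 5 to 13 subjects each, so the corrected contrast will be imprecise. That limits what can be learned from it, but does not justify a comparison that is biased in a known direction.

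**Conclusion.** The point holds for the comparison as stated in Protocol 7.2, and no visible text replaces it. The direction of the bias follows from using one error-prone score for both selection and baseline. Its size rests on assumptions: about 3 to 4 CAPS-5 points in raw change (1.3 to 8.7 under wider inputs), and about 1 to 1.5 points (0.4 to 3.6) after adjustment for the Week 4 score.

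The label is a lesser matter. It would be too strong to say that arms 4 to 6 hardly improved on placebo: under most of the assumed inputs, most responders exceed a 35% reduction. A minority do not, roughly 13% to 32%, and up to 68% under the wider inputs. Nor is the trial's main result affected: the primary and secondary analyses use arms 1 to 3 and 7 to 9, and the Stage 2 part of those compares drug with placebo inside one stratum.

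**What to change.** In Protocol 7.2 and the SAP's exploratory analyses:

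- Replace the comparison of arms 5 and 6 with arms 8 and 9 by drug-minus-placebo contrasts within each stratum: arms 5 and 6 against arm 4, and arms 8 and 9 against arm 7.
- Compare the strata only through the difference of those contrasts, with confidence intervals. The two doses may be pooled, given the arm sizes.
- Label the result exploratory and imprecise.
- Describe arms 4 to 6 as subjects who did not meet the non-responder rule, and report how many had a Day 1 to Week 4 reduction of 35% or less. A count is enough; the arms are too small to need a further formal split.

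If Protocol 14.4.1.3 or the SAP 8.3 subsections that are not visible already contain these contrasts, only the sentence in Protocol 7.2 needs aligning. The cost is wording plus one exploratory contrast on data already collected. The primary analysis and the re-randomisation rule do not change.
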